## 6.2. Covariates

In the multivariate analyses comparing the two treatment groups, age, gender, weight, BMI, race/ethnicity, smoking classification collected as current smoker, ex-smoker, or non-smoker, alcohol usage (yes/no), hepatitis status, history of cardiovascular disease, screening HIV-1 RNA levels, and screening CD4+ cell counts will be used as covariates as appropriate. If data is available for other relevant covariates (for example: the use of lipid lowering agents), these will also be utilized.

## 7. HANDLING OF MISSING VALUES

For the analysis of safety, Pfizer Data Standards (PDS) rules for imputation will be applied. Missing dates for study medication, and adverse events (AE's) will be imputed using the PDS algorithm.

## 8. STATISTICAL METHODOLOGY AND STATISTICAL ANALYSES

### 8.1. Efficacy and Pharmacokinetic Analysis

None

## 8.2. Safety Analyses

All safety data will be subjected to clinical review and summarized according to Pfizer Data Standards and using the Safety Analysis Set. The format and algorithms described in Pfizer Data Standards documentation will be followed to produce summary tables and listings.

This study will provide data to calculate incidence rates on each of the study endpoints in the two study groups and will be analyzed as given below:

1. Descriptive statistics (ie, frequency, percent, mean, median, standard deviation as appropriate depending on data type) will be used to summarize characteristics (clinical and demographic) of patients enrolled in the study. (Potential variables include but are not limited to age, gender, weight, BMI, race, smoking classification, alcohol use (yes/no), HIV-1 RNA level, CD4+ T lymphocyte counts, duration of antiretroviral therapy, duration of HIV infection, number of failed regimens etc.).
2. Cumulative incidence rates and incidence-density rates of the study endpoints in the two groups will be reported along with respective 95% confidence intervals.
3. Subject discontinuation, loss to follow-up and total person-time of follow-up accrued in the study will be summarized.
4. Depending on data availability, appropriate subgroup analyses may be performed to further describe the rates of the study endpoints stratified by age group, gender, baseline CD4+ cell counts, baseline viral load, hepatitis C/hepatitis B serology, duration of maraviroc use, total duration of antiretroviral use, components of OBT etc.
5. In addition to the study endpoints, SAEs and drug-related adverse reactions reported during the study will be summarized in tables and listings.
6. Crude and adjusted rate ratios with 95% confidence intervals will be calculated for each study endpoint comparing maraviroc-exposed patients to maraviroc-unexposed patients. Multivariate analysis techniques will be used as appropriate (e.g., Poisson regression model) to account for the baseline difference in the two study groups via propensity score technique. Specifically, since subjects are not randomized to treatment, there is a potential for imbalance in the above-mentioned important demographic and baseline characteristics between groups. To account for the imbalance between the two groups on the clinically important demographic and baseline characteristics, the confidence intervals will be adjusted for propensity score quintile. Specifically, propensity score for treatment membership (maraviroc exposed vs. maraviroc un-exposed) will be calculated for each subject from a logistic regression with the above mentioned covariates as predictors and study group membership as the outcome. Participants with similar propensity scores generally have similar distribution of the covariates on which the score is based. Participants will then be categorized into quintiles according to their propensity score. Four indicator variables will be created to represent the propensity score quintiles and will be used in the multivariate model as covariates along with the primary exposure variable i.e., exposure to maraviroc. Adjusting for propensity score quintile in this manner helps account for imbalances at baseline as discussed in D'Agostino (1998).
7. Appropriate survival analyses techniques (eg, Kaplan-Meier survival curves, Cox proportional hazards model) will be used to further analyze the data. The multivariate models will incorporate appropriate techniques referred to in section 4.2.3 to adjust for

potential survival bias.

8. In addition, incidence rates in patients receiving maraviroc in this study may be compared to those reported in comparable patients (ie, those with similar propensity scores and with the smallest Mahalanobis' distance between baseline values (D'Agostino, 1998) not using maraviroc in other HIV-1 infected cohort(s) such as EuroSIDA. The baseline characteristics of the patients (eg, number of failed regimens, CD4+ T lymphocyte counts) in this study will be used to identify comparable subjects from the external cohort(s).

The following data will be presented in standard safety summaries:

- *adverse events*
- *laboratory data (to the extent available)*
- *vital signs data (pulse rate, systolic and diastolic blood pressure)*

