9.1. Sample Size

The sample size for the study was determined based on an extensive feasibility assessment in 28 countries, input from Pfizer country offices, and in consultation with the regulators. This number was estimated to be 3,000 subjects (1,500 patients receiving maraviroc and

1,500 patients not receiving maraviroc) to allow calculations of reliable and precise risk estimates.

Malignancies, myocardial ischemia or infarction and deaths (liver-related and all cause) occurring at any time during the 5-year follow-up period will be adjudicated and analyzed as study endpoints. Assuming up to 10% annual loss to follow-up, the 1,500 patients each receiving maraviroc or the anchor drug will contribute 5,836 person-years of observation for these study endpoints over a 5-year period (See Scenario 1 in [Appendix 3](#) for details) in each treatment arm. It is assumed that the expected incidence rates are 12.7 per 1000 person-years for malignancies,¹⁴ 3.5 per 1,000 person-years for myocardial infarction,¹³ 2.35 per 1,000 person-years for liver-related deaths,¹⁵ and 16 per 1,000 person-years for all cause mortality¹⁵ in the internal comparator group of patients not receiving maraviroc.

CDC category C AIDS-defining opportunistic infections, viral encephalitis, rhabdomyolysis and liver failure will be adjudicated and analyzed as study endpoints if they occur during the use of maraviroc or the anchor drug in the OBT arm or within 6 months following maraviroc or anchor drug discontinuation. Accounting for the expected rates of drug discontinuation in the two treatment arms over time and a 10% annual loss to follow-up, each study arm will accrue 2,875 person-years of observation for these study endpoints (See Scenario 2 in [Appendix 3](#) for details). It is assumed that the expected incidence rates are 3.5 per 1,000 person-years for liver failure,¹⁶ and 160 per 1,000 person-years for AIDS-defining opportunistic infections¹⁷ in the internal comparator group of patients not receiving maraviroc.

Based on these assumptions of equal person years of contribution in the maraviroc exposed and unexposed groups, using a two-tailed test with $\alpha=0.05$, and a power of 80%, the minimum detectable relative rates for various study end points are reported in Table 2.¹⁸

Table 2. Minimum detectable relative rates using a two sided test, $\alpha =0.05$, and a power of 80%

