### 2.1. Study Design

*This is an international, multicenter, open-label, comparative, prospective observational epidemiologic study.*

*The study will enroll 1500 HIV-1 infected, treatment-experienced adult patients who have been prescribed maraviroc along with an optimized background antiretroviral therapy (OBT) regimen in usual clinical practice following the approved local label of maraviroc.*

*The internal comparator group will consist of 1500 HIV-1 infected, treatment-experienced adult patients receiving OBT who received an HIV-1 tropism assay as a screening test for eligibility to receive maraviroc in usual clinical practice but were not prescribed maraviroc. This group may include patients infected with dual/mixed tropic or CXCR4 tropic HIV-1 as well as patients infected with CCR5 tropic HIV-1.*

The subject enrollment scheme is presented in [Appendix 2](#).

The study will be conducted at approximately 300 sites in multiple countries. Participating countries were chosen on the basis of extensive feasibility assessments and include: Belgium, Brazil, Canada, France, Germany, Greece, Italy, Portugal, Spain, United Kingdom, and United States. If required, additional countries may be added and some countries in this initially proposed list may be dropped. Countries will participate only after maraviroc is approved by Health Authorities in that country and is commercially available. Enrollment will be competitive and recruitment of subjects will terminate after the global target sample size is achieved. The expected numbers of subjects in the participating countries are provided in Table 1. Initial enrollment goals set for each country will be redistributed if necessary. Barring unforeseen circumstances (eg, significant delays in marketing authorization approval in countries, marked delays in regulatory approvals of the study protocol in countries, etc.), enrollment is expected to commence in 1Q2008 and is anticipated to continue for approximately 30 months. The enrollment status will be continuously monitored by the Sponsor and the external Scientific Steering Committee overseeing the study. If required, the enrollment period will be extended to enroll the necessary sample size.

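### As SAP 8.2 item 6 is written, adjustment by propensity quintile alone leaves some CD4 and HIV-1 RNA confounding in the rate ratios; direct terms for both would be a cheap improvement

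*SAP*

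**What the plan says.** SAP 8.2 item 6 is the only place that explains how the adjusted rate ratio is built. The score comes from a "logistic regression with the above mentioned covariates as predictors and study group membership as the outcome". Subjects are then cut into quintiles of the score: "Four indicator variables will be created to represent the propensity score quintiles and will be used in the multivariate model as covariates". The other term in that model is exposure to maraviroc.

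SAP 6.2 lists the covariates for the comparative multivariate analyses. The list includes age, smoking, hepatitis status and others, and says "screening HIV-1 RNA levels, and screening CD4+ cell counts will be used as covariates as appropriate". It does not say whether they enter the outcome model directly or only through the score. SAP 8.2 item 7 adds Cox models without listing covariates. Protocol 9.2 says only that multivariate techniques will be used as appropriate.

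On the comparator, SAP 2.1 says: "This group may include patients infected with dual/mixed tropic or CXCR4 tropic HIV-1 as well as patients infected with CCR5 tropic HIV-1". SAP 4.1 states no statistical hypotheses.

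**The concern.** Someone programming item 6 literally would fit exposure and four indicators, and nothing else. Within a quintile the score still varies, so the arms can still differ in CD4 and viral load, and both plausibly predict OI. Item 6 itself recognises that non-randomised groups may be imbalanced, and the two arms can differ in viral tropism.

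OI is the endpoint most exposed to this because it has the most events. A standard error of about 0.066 on the log scale is small enough for a bias of a few percent to matter. If comparators are sicker, the residual bias pulls the ratio down and can hide an excess risk. If maraviroc patients are sicker, it pulls the ratio up and produces false alarms.

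**Working it through.** **Inputs from Protocol 9.1 and Table 2.** OI rate "160 per 1,000 person-years for AIDS-defining opportunistic infections"; "each study arm will accrue 2,875 person-years of observation for these study endpoints"; two-sided alpha 0.05; detectable rate ratio 1.1955 at 80% power.

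**Reproducing the plan's figure.**
- Comparator events: 0.160 x 2,875 = 460.
- Standard error of the log rate ratio with no effect: sqrt(2/460) = 0.066.
- Standard error at 1.1955: sqrt(1/460 + 1/(460 x 1.1955)) = 0.0632.
- Power: Phi(0.1786/0.0632 - 1.96) = 80.7%, where 0.1786 = ln(1.1955). The stated 80% reproduces.

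**Share of bias that quintiles leave (assumed confounding).** Large-sample Poisson models were fitted with treatment assigned by a logistic function of CD4 and RNA, and with a log-linear or threshold effect of CD4 on OI. Quintile indicators alone left 8-20% of the crude log bias, mostly 9-15%. Correctly specified CD4 and RNA terms left none. A linear CD4 term, when the true effect was not linear in CD4, left 2-3%.

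**What that does to the OI result.** Let c be the crude confounding ratio, meaning the crude rate ratio that would appear with no drug effect. Let s be the share left.
- Residual ratio = c^s.
- Power at 1.1955 = Phi((0.1786 + s x ln c)/0.0632 - 1.96).
- With d = |s x ln c|/0.066, coverage at no effect = 1 - Phi(-1.96 + d) - Phi(-1.96 - d).

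With s = 0.11 to 0.14:

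| c | residual ratio | power at 1.1955 | 95% interval coverage |
|---|---|---|---|
| 0.95 | 0.994-0.993 | 78-77% | 94.9% |
| 0.90 | 0.988-0.985 | 75-74% | 94.6-94.4% |
| 0.80 | 0.976-0.969 | 68-65% | 93.4-92.4% |
| 0.70 | 0.962-0.951 | 60-53% | 90.9-88.2% |
| 0.60 | 0.945-0.931 | 49-40% | 86.4-80.8% |
| 1.25 | 1.025-1.032 | 90-91% | 93.4-92.4% |

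The wider share of 8-20% widens each row. At c = 0.90 the residual ratio is 0.992-0.979 and power 77-70%. At c = 0.70 they are 0.972-0.931 and 66-40%.

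**Effect of the fix.** 3,000 patients, 600 replicates per scenario, true ratio 1.1955, simulation error up to about 2 points. Here c is the mean crude estimate divided by 1.1955.

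| c | power, quintiles only | power, quintiles + CD4 + RNA |
|---|---|---|
| no imbalance | 78% | 79% |
| 0.95 | 77% | 81% |
| 0.90 | 68% | 74% |
| 0.84 | 65% | 74% |
| 0.73 | 44% | 70% |
| 0.62 | 31% | 66% |

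With the direct terms the mean estimate was 1.189-1.198, against 1.115-1.191 for quintiles only in the five imbalanced scenarios. Power stays below 80% under stronger imbalance because imbalance also raises the standard error (0.063 with none, 0.075 in the last row). The formula above holds the standard error at 0.0632, so it is somewhat kinder than the simulation.

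**The case against.** Quintile adjustment is a recognised, referenced method. SAP 6.2 names CD4 and HIV-1 RNA for the comparative multivariate analyses, item 7 allows further models, and item 4 allows subgroup rates by baseline CD4 and viral load. So it is too strong to say that the plan rules out direct adjustment. That stands. But none of these passages commits to direct terms, and the only model spelled out omits them.

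The size is also assumed: no passage gives a baseline difference between arms or a CD4-OI gradient. That stands too, and several stronger readings fail because of it:

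- A reader might infer that comparators must have lower CD4 because they may carry CXCR4-using virus. Protocol 1.2.2 ties that virus to late disease or treatment experience. Both arms are treatment-experienced, and the comparator may include CCR5-tropic patients, so neither size nor direction follows.
- A reader might infer a marked power loss as a property of the plan. Power near 40% needs strong confounding (c about 0.6 at a 14% share). Under mild confounding the loss is about 3-7 points, and in the reverse direction power to declare harm rises.
- A reader might suppose that most OI events fall in the extreme quintile. Simulation put 27-47% there.
- A reader might frame this as inflated type I error. With no stated hypotheses, bias and interval coverage are the better frame.

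**Conclusion.** The point holds in a conditional form. Item 6, followed as written, is a specified method that leaves part of the CD4 and HIV-1 RNA confounding in place: about 8-20% of the crude log bias under assumed scenarios.

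For OI, at an 11-14% share, the bias is about 0.6-1.5% for a crude confounding ratio of 0.90-0.95 and about 2.4-6.9% for 0.6-0.8. Coverage is correspondingly close to 95% in the mild case and between about 93% and 81% in the stronger one. The direction is unknown.

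It would be wrong to conclude that direct terms remove the problem outright. They act only on these two variables, need them observed and sensibly modelled, and do not recover the precision lost to imbalance. This is a cheap improvement to the plan; it does not invalidate the planned analysis.

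**What to change.** In SAP 8.2 item 6, keep the four quintile indicators and add screening CD4 (square-root or flexible form) and log10 HIV-1 RNA as continuous covariates in the outcome model for OI, malignancy and all-cause death. Leave the rarer endpoints (Table 2 expects 10-20 comparator events) as planned. Add a cross-reference in SAP 6.2 so that the two sections agree on how these covariates are used.

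The cost is about one sentence and two or a few extra parameters, in models with at least 74 expected comparator events (Table 2). No new data are needed. Protocol 7.2 mandates no laboratory tests, so some CD4 or RNA values may be missing, but the propensity score already uses both variables and faces the same gap. The SAP should state one handling rule for both uses.

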### **8.2.1. Treatment and Disposition of Subjects**

Subject evaluation groups will show the end of study subject disposition and will report which subjects were analyzed for safety (adverse events). Frequency counts will be supplied for subject discontinuation(s).

### **8.2.2. Demographic and Clinical Examination Data**

Demographic information including age, gender, weight, BMI, race/ethnicity, smoking classification, alcohol use, percentage of patients with AIDS defining events, HIV-1 RNA level, and CD4+ cell counts at screening/baseline or at the time of entry into the study will be described. Age will be derived from the visit date and the date of birth according to the Pfizer Data Standards algorithm.

Continuous measurements like age, height, weight, and duration of HIV-1 will be summarized using the descriptive statistics (N, mean, standard deviation, median, range).

Categorical data like gender, race, smoking classification, and alcohol use (yes/no) will be summarized by counts (N, frequency, and percent).

### **8.2.3. Discontinuation(s)**

Discontinuation of maraviroc or the anchor drug (as applicable) due to adverse events or abnormal laboratory test results will be detailed and summarized by maraviroc exposed and un-exposed groups. In addition, subjects who permanently withdrew from the study will also be summarized.

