6.3. Follow-up of patients discontinuing maraviroc

If a patient discontinues maraviroc, the enrolling physician will record information on the date of and primary reason for discontinuation. Discontinuation of maraviroc due to adverse events should be distinguished from discontinuation due to insufficient response, and any serious adverse events (SAE) should be reported immediately to Pfizer, as the Sponsor's designated representative. A change in any of the components of OBT will not be considered as treatment discontinuation if the patient continues to receive maraviroc, but these changes in regimen will be recorded on patient questionnaires by enrolling physicians. Follow-up will continue after a patient discontinues maraviroc up to a total period of 5 years since enrollment, and safety data will be collected and reported for a total of 5 years following enrollment as well.

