7.3. Follow-up Data

Follow-up information on the study outcomes, adverse events, laboratory tests, medication use, other relevant clinical information and the patient's vital status will be abstracted on follow-up questionnaires by the enrolling physician or a designated member of the clinical team from medical records and charts as well as from the patient, where applicable.

The complete follow-up questionnaires will be electronically submitted after a patient returns for follow-up according to local HIV treatment guidelines and routine medical practice (usually 3-4 monthly), and at least once every 6 months. At these visits, the physician will treat the patient per standard clinical practice and will conduct laboratory investigations as appropriate. **There will be no study-mandated tests or interventions.** Data on the patient's medications, recent laboratory test results and the study endpoints since the last visit/report will be recorded in the follow-up questionnaires based on the source medical records.

If a patient does not return for follow-up within six months from last contact, the enrolling physician will make at least three attempts to contact the patient to return for routine follow-up. If these initial attempts to directly contact the patient fail, the alternate contact person(s) recorded on file will be contacted to ascertain the whereabouts and survival status of the patient.

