Study endpoints that are closely temporally related to drug exposures ie, CDC category C opportunistic infections, viral encephalitis, rhabdomyolysis and liver failure will cease to be adjudicated as study endpoints after six months following discontinuation of maraviroc. For patients in the maraviroc unexposed comparator group, adjudication of these events will cease after six months following discontinuation of the anchor drug in their OBT as identified at baseline (Section 7.2). If these events are diagnosed after this cut-off period, they will be considered as any other adverse event and reported per the Adverse Event Reporting guidelines described in Section 8, which requires the collection and reporting of all serious adverse events (SAE) and all adverse reactions. Occurrence of myocardial infarction or ischemia, malignancies, and death (all-cause and liver-related) will be reported and adjudicated as study endpoints for up to five years following enrollment.

The follow-up duration for malignancies may be extended beyond five years if, based on emerging safety data, the Scientific Steering Committee (SSC) overseeing the study recommends a longer period of observation. Due to the potentially prolonged time required for a malignancy to become clinically apparent, a search of national and state cancer and death registries will be performed to look for all episodes of malignancy within 10 years of study entry for all subjects in countries where such registries are available, are accessible for research purposes and where such search is allowed by local law. Active study participation of subjects will be for only 5 years, but informed consent will be obtained at enrollment allowing for passive subject follow-up beyond the 5 years of active participation through this additional search of cancer and vital status registries. This search will be conducted by a designated CRO or professional search firm using appropriate national identifiers collected at enrollment. The investigators will not have to do the search.

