8.1. ADVERSE EVENTS

All observed or volunteered serious adverse events (SAE) regardless of treatment group or suspected causal relationship to maraviroc and all non-serious adverse events suspected by the investigator to be related to maraviroc (ie, adverse reactions) will be recorded on the adverse event page(s) of the case report form (CRF) as follows.

For all adverse events, the investigator must pursue and obtain information adequate both to determine the outcome of the adverse event and to assess whether it meets the criteria for classification as a serious adverse event (see section "Serious Adverse Events") requiring immediate notification to Pfizer as the Sponsor's designated representative. For all adverse events, sufficient information should be obtained by the investigator to determine the causality of the adverse event. The investigator is required to assess causality. For adverse events with a causal relationship to maraviroc, follow-up by the investigator is required until

09017e1928d33f51Approved Approved On: 07-Jan-2020 12:23 (GMT)

the event or its sequelae resolve or stabilize at a level acceptable to the investigator, and Pfizer on behalf of the Sponsor concurs with that assessment.

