### **8.2.4. Adverse Events**

All serious adverse events regardless of their association with maraviroc will be collected and summarized by the treated group.

Maraviroc related non-serious adverse events (AE's) are collected in this observational study and will be reported according to the Pfizer Data standards (PDS).

- Maraviroc related study emergent AE's by Body System
- Incidence and Severity of maraviroc related study Emergent AE's
- Discontinuation of maraviroc due to Adverse Events

**Note:** If for some reason an investigator reports non-serious adverse events in the maraviroc un-exposed group, these will be summarized descriptively (if applicable).

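### SAP 8.2.3 tabulates drug stops for toxicity by group, but the protocol requires the reason for stopping only for maraviroc, so comparator stops for non-serious toxicity are liable to be undercounted

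*SAP*

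**What the plan says.** **The planned table.** SAP 8.2.3 states: "Discontinuation of maraviroc or the anchor drug (as applicable) due to adverse events or abnormal laboratory test results will be detailed and summarized". The presentation is side by side: "summarized by maraviroc exposed and un-exposed groups". SAP Section 3 adopts the Section 8.2 analyses for the yearly progress reports to regulatory agencies, so this table would be reported repeatedly.

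**Reason for stopping.** Protocol 6.3 states: "If a patient discontinues maraviroc, the enrolling physician will record information on the date of and primary reason for discontinuation". It adds: "Discontinuation of maraviroc due to adverse events should be distinguished from discontinuation due to insufficient response". Both sentences concern maraviroc only.

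**The anchor drug.** Protocol 7.4 uses the stop to end adjudication of the exposure-related endpoints: "adjudication of these events will cease after six months following discontinuation of the anchor drug in their OBT as identified at baseline". It does not ask why the drug was stopped. Protocol 7.3 says of follow-up in both arms: "Data on the patient's medications, recent laboratory test results and the study endpoints since the last visit/report will be recorded in the follow-up questionnaires".

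**Adverse events.** Protocol 8.1 collects SAEs in every subject, whatever the group or suspected cause. Beyond these it collects "all non-serious adverse events suspected by the investigator to be related to maraviroc", and Protocol 8.9.2 repeats that limit. SAP 8.2.4 treats other cases as exceptional ("If for some reason an investigator reports non-serious adverse events in the maraviroc un-exposed group") and lists a table of stops due to adverse events for maraviroc only.

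**The concern.** A by-group count of toxicity stops can be read only if the reason for stopping is obtained in the same way in both groups. Here one group has a required reason, with adverse events kept apart from insufficient response. The other has no stated requirement. The usual back-up, the adverse event record, is uneven in the same direction, because a comparator who has never taken maraviroc cannot have a non-serious event suspected to be related to it.

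The study is a post-approval safety commitment to two regulators (Protocol 1.2.5). A table that shows more toxicity-related stopping on maraviroc because of how reasons are recorded could be taken for a tolerability signal.

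**Working it through.** The documents give no figure for stops due to toxicity, so there is nothing to reproduce. The check has two parts: tracing the data routes, and an illustration on assumed inputs.

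**Routes into the SAP 8.2.3 table**

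1. *Stated reason for stopping the drug.* Maraviroc: required (Protocol 6.3). Anchor drug: not required in any section of either document.
2. *SAE record.* Required in both arms (Protocol 8.1).
3. *Non-serious adverse event record.* Maraviroc: required if suspected to be related. Comparator: not required (Protocol 8.1, 8.9.2; SAP 8.2.4).
4. *Abnormal laboratory finding.* Protocol 8.4 says when such a finding counts as an adverse event, but the limit in 8.1 still governs whether a non-serious one is reported. Protocol 7.3 records recent laboratory values in both arms, without linking them to a drug change.
5. *Medication record.* Protocol 7.3 covers both arms. It can show that a drug stopped and when, but no reason is listed.
6. *Withdrawal record.* Protocol 6.7 asks for the reason when consent is withdrawn. It does not cover a comparator who stops the anchor drug and stays in the study.

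Route 2 is the only one that is both required in the two arms and able to indicate toxicity. A comparator stop for non-serious toxicity therefore has no required route.

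**Illustration of size (assumed inputs)**

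Let *q* be the true proportion stopping for toxicity, equal in both arms. Let *s* be the share of those stops linked to an SAE, all identified in both arms. Let *c* be the share of the remaining comparator stops that is captured anyway. Maraviroc capture is taken as complete. Then

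- observed comparator proportion = *q* × [*s* + (1 − *s*)*c*]
- apparent ratio, maraviroc to comparator = 1 / [*s* + (1 − *s*)*c*]

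The ratio does not depend on *q*. For counts, take *q* = 10% (assumption) and 1,500 per arm (SAP 4.2.1), so the true count is 0.10 × 1,500 = 150 in each arm.

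No other capture (*c* = 0):

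- 25% non-serious (*s* = 0.75): 150 × 0.75 ≈ 113 comparator stops seen; ratio 1/0.75 = 1.33
- 50% non-serious (*s* = 0.50): 150 × 0.50 = 75; ratio 1/0.50 = 2.0
- 75% non-serious (*s* = 0.25): 150 × 0.25 ≈ 38; ratio 1/0.25 = 4.0
- all SAE-linked (*s* = 1): 150; ratio 1.0

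Half of the non-serious comparator stops captured anyway (*c* = 0.5):

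- *s* = 0.75: 150 × 0.875 ≈ 131; ratio 1.14
- *s* = 0.50: 150 × 0.75 ≈ 113; ratio 1.33
- *s* = 0.25: 150 × 0.625 ≈ 94; ratio 1.6

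**The case against.** **The forms are not in the documents.** The protocol is silent on the anchor-drug reason and does not forbid collecting it. Protocol 7.3 names adverse events and other relevant clinical information without restriction by arm, and the authors of SAP 8.2.3 may have had a reason field in mind. This stands. A reader might infer that comparator stops will certainly be undercounted; the text supports only that they are liable to be.

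**The table is descriptive.** A reader might infer a biased comparison of study endpoints. That is not supported. SAP 4.1 states no hypotheses, the rate ratios in SAP 8.2 are for study endpoints, and drug discontinuation is not one of them. The risk is a misread safety table. It remains a risk, because the counts are shown side by side.

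**Total stopping is not toxicity stopping.** Appendix 3's rates of 30% and 25% for the first two six-month periods give 1 − 0.70 × 0.75 = 47.5%, or about 713 of 1,500 comparators in year 1, ignoring losses. A reader might take this as the number of missed toxicity stops. It counts stops for any cause, on rates taken from the maraviroc programme and applied to both arms. Nor do the documents give a share of non-serious stops from which to fix a large ratio.

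**The adjudication windows.** A reader might infer that missing reasons distort the opportunistic infection, viral encephalitis, liver failure and rhabdomyolysis endpoints. They do not affect the definition: the window closes six months after the drug stops, whatever the cause, so only the date matters.

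**Conclusion.** The mismatch between SAP 8.2.3 and the protocol's collection rules is real, and its direction follows from the text. Non-serious toxicity stops on maraviroc are captured by rule, and those on the anchor drug only if a site or form happens to record the reason. SAP 8.2.4, which tabulates adverse-event stops for maraviroc only, also does not match 8.2.3.

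The size is unknown. The illustrative ratios of 1.33 to 4 rest on equal true rates, complete capture for maraviroc, no incidental capture for comparators, and a non-serious share of 25% to 75%; none of these is a document value. The bias shrinks with any incidental capture and vanishes if every toxicity stop is linked to an SAE. It is confined to this descriptive table and is cheap to remove.

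**What to change.** - **Protocol 6.3:** extend the requirement so that the date and primary reason are recorded when a patient stops maraviroc or the anchor drug identified at baseline. Use the same categories in both arms: adverse event or abnormal laboratory test, insufficient response, other. If the questionnaire already has such a field for both drugs, the protocol need only state it.
- **SAP 8.2.3:** build the table from that field together with SAE data. Using the reason field alone would discard the one adverse event source already required in both arms.
- **Comparator stops with no recorded reason:** limit the by-group summary to SAE-linked stops, show the rest as *reason not collected*, and present non-serious toxicity stops for maraviroc only, with no between-arm contrast.
- **SAP 8.2.4:** align its discontinuation table with 8.2.3.

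The cost is a short protocol amendment, a small SAP change and slightly more data entry at sites. Reasons for earlier comparator stops will remain incomplete. The change concerns data capture and presentation only.
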